### 11.5 Patient Compliance

All patients will receive study drug under direct observation by the site personnel. Dosing date

NCI Protocol #: 7870

Protocol Version Date 5/29/19

page 55 of 79

and time will be recorded by the site staff on the CRF. For all other doses, the patient will self-administer his/her dose of oral medications per schedule and record the date and time in the patient diary. If a patient regurgitates any tablets, the patient should not repeat that dose, but should resume his/her scheduled subsequent doses.

Pill counts will be utilized to monitor compliance as well as the patient diary. Patients will be supplied with a diary in which to record the date and time of each self-administered dose of study drugs. Patients will also be asked to record any partial doses. Study site staff will review the diary with the patient at each scheduled clinic visit and transcribe all pertinent information onto the CRF. The diaries will be retained at the study site as part of the source documentation and new diary pages issued to the patient following each visit. Patients will be asked to return all study medication bottles (empty, partial or full) to the study staff.

### **11.6 Data quality assurance**

This study will be monitored regularly. Monitoring procedures include one or more visits designed to clarify all prerequisites before the study commences. Interim monitoring visits will take place on a regular basis according to a schedule fixed by mutual agreement. During these visits, the CRA will check for completion of the entries on the CRFs, their compliance with the study protocol and with GCP, and will compare the CRF entries with the source data.

For source data verification, at least the following information must be included in the patient note/file:

- Date of patient's written informed consent,
- Patient participation in a clinical study and the study number,
- Patient visit dates,
- Serious adverse events,
- Adverse events,
- Confirmation of the diagnosis of the indication being treated,
- Study drug administration (e.g., start of study treatment, dose),
- Concomitant disease medications and dose (including parenteral nutrition and corticosteroid dose), and
- Primary endpoint.

The CRA will collect the appropriate copy or copies of the completed forms. He/she will also verify the correct use of the investigational product. Entinostat will not be supplied to the investigator site prior to approval from the IRB/IEC and regulatory authority (if applicable). At a final visit, the CRA will check all remaining material including the remaining quantities of the investigational product and will organize its return.

In addition, the CRA will determine whether all AEs and SAEs have been appropriately documented and whether the SAEs were reported within the time periods required.

A member of the Quality Assurance Unit may arrange to visit the investigator in order to audit the performance of the study at the study site and the study documents originating there. A sponsor designee will usually accompany the auditors. The investigator will be informed about the outcome of the audit.

## **11.7 Reporting and Exclusion**

### **11.7.1 Evaluation of toxicity**

All patients will be evaluable for toxicity from the time of their first dose of entinostat

### **11.7.2 Evaluation of response**

All conclusions should be based on all eligible patients who initiate entinostat treatment. Sub-analyses may then be performed on the basis of a subset of patients, excluding those for whom major protocol deviations have been identified (e.g., early death due to other reasons, early discontinuation of treatment, major protocol violations, etc.).

However, these sub-analyses may not serve as the basis for drawing conclusions concerning treatment efficacy, and the reasons for excluding patients from the analysis should be clearly reported.

Prolonged lymphocyte decrease is not considered a DLT since it is a known side effect of high dose interleukin 2 and it is not considered clinically relevant.

Enrolled patients who are deemed to be not eligible/not evaluable will be replaced.

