### **9.2.7 Reporting of results**

- All patients included in the study must be assessed for response to treatment, even if there are major protocol treatment deviations or if they are ineligible. Each patient will be assigned one of the following categories: 1) complete response, 2) partial response, 3) stable disease, 4) progressive disease, 5) early death from malignant disease, 6) early death from toxicity, 7) early death because of other cause, or 8) unknown (not assessable, insufficient data).
- All of the patients who met the eligibility criteria should be included in the main analysis of the response rate. Patients in response categories 4-8 should be considered as failing to respond to treatment (disease progression). Thus, an incorrect treatment schedule or drug administration does not result in exclusion from the analysis of the response rate. Precise definitions for categories 4-8 will be protocol specific.
- All conclusions should be based on all eligible patients.
- Sub-analyses may then be performed on the basis of a subset of patients, excluding those for whom major protocol deviations have been identified (e.g., early death due to other reasons, early discontinuation of treatment, major protocol violations, etc.). However, these sub-analyses may not serve as the basis for drawing conclusions concerning treatment efficacy, and the reasons for excluding patients from the analysis should be clearly reported.
- The 95% confidence intervals should be provided

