### **11.7.3 Discontinuation and Withdrawal of Subjects**

**11.7.3.1** All patients who initiate protocol treatment will be included in the overall evaluation of response (intent-to-treat analysis). All reasons for discontinuation of treatment should be documented clearly in the medical record. Note: Patients who sign a consent form, but do not initiate study drug will be replaced.

**11.7.3.2** Non-compliance with the study protocol; including, but not limited to not attending the majority of scheduled visits. The PI will determine when non-compliance should lead to removal from study. Note: The patients will still be included in the overall evaluation of response (intent-to-treat analysis)

**11.7.3.3** Unacceptable major toxicity. Note: The patients will still be included in the overall evaluation of response (intent-to-treat analysis).

**11.7.3.4** At patient's own request. Note: The reason for discontinuation from the study must be documented. The patients will be included in the overall evaluation of response (intent-to-treat analysis) if any protocol therapy was administered prior to withdrawal.

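### Section 11.7.2 lets patients who are not eligible or not evaluable be replaced even after dosing, while the cutoff of 11 responders is set for exactly 36 treated patients

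*Combined protocol and SAP*

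**What the plan says.** Section 11.3 (Phase II, Primary Objective) plans for 36 new patients to be treated at the recommended dose. It rejects a response rate of 20% or less if at least 11 respond. The stated type I and type II errors are both 0.09, against targets of 10% each. No cutoff is given for any other number of patients.

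Two passages deal with replacement:

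- Section 11.7.2: "Enrolled patients who are deemed to be not eligible/not evaluable will be replaced".
- Section 11.7.3.1: "Patients who sign a consent form, but do not initiate study drug will be replaced".

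The analysis set is described in three places:

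- Section 9.2.7: "All of the patients who met the eligibility criteria should be included in the main analysis of the response rate". The possible outcomes include "8) unknown (not assessable, insufficient data"), and "Patients in response categories 4-8 should be considered as failing to respond to treatment (disease progression").
- Section 11.7.2: "All conclusions should be based on all eligible patients who initiate entinostat treatment".
- Section 11.7.3.1: "All patients who initiate protocol treatment will be included in the overall evaluation of response (intent-to-treat analysis"). Section 11.7.3.4 also keeps patients who withdraw at their own request "if any protocol therapy was administered prior to withdrawal".

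Section 4.1 starts entinostat on day -14 and puts the response assessment at week 11.

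**The concern.** The replacement sentence in 11.7.2 is broader than the one in 11.7.3.1. It covers enrolled patients in general, and it does not say what makes a patient not evaluable for response. Because entinostat starts well before the week 11 scan, a patient can be dosed and leave with no response assessment. Read literally, 11.7.2 allows that patient to be replaced.

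Two kinds of treated patient need to be kept apart.

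- **Treated, with no assessable response.** Such a patient cannot add a responder, so counting or dropping the patient leaves the responder total unchanged. The replacement is what matters, because it gives a further chance to reach 11.
- **Treated, later found ineligible.** Such a patient can respond, so counting or dropping the patient does matter. Sections 9.2.7 and 11.7.2 analyse eligible patients only, whereas 11.7.3.1 analyses everyone who starts treatment. Two analysts following different sections would report different denominators and possibly different numbers of responders.

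The cutoff of 11 is the trial's primary go/no-go rule, and its planned type I error lies only about 0.011 below the target.

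**Working it through.** **Inputs.** From section 11.3: N = 36, cutoff 11, null rate 0.20, target rate 0.40, exact binomial test. The number of treated patients replaced, k, is not in the documents. It is an assumption, shown here for 1 to 4.

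**The plan's own figures.**

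- Type I error: P(X ≥ 11 | 36, 0.20) = 0.0889.
- Type II error: P(X ≤ 10 | 36, 0.40) = 0.0904.

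Both round to the stated 0.09, so the design reproduces.

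**Case A: k treated patients with no assessable response are replaced.** In total 36 + k are treated, and 36 can respond. Suppose the 20% null holds in all treated patients and the k replaced patients are certain non-responders. The rate among the other 36 is then 0.20 × (36 + k)/36, and the type I error is P(X ≥ 11 | 36, that rate).

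| k | Rate among the 36 | Type I error |
|---|---|---|
| 0 | 0.2000 | 0.089 |
| 1 | 0.2056 | 0.104 |
| 2 | 0.2111 | 0.120 |
| 3 | 0.2167 | 0.138 |
| 4 | 0.2222 | 0.158 |

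The same can be put as a probability q that a treated patient is unassessable. The rate becomes 0.20/(1 − q), and the type I error is 0.0997, 0.1185 and 0.1577 at q = 0.02, 0.05 and 0.10. It equals 0.10 at q = 0.0204.

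If the 20% null applies to evaluable patients only, the rate stays 0.20 and the type I error stays 0.089.

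**Case B: k treated ineligible patients are replaced.** They can respond.

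- Counted, as in 11.7.3.1: P(X ≥ 11 | 36 + k, 0.20) = 0.105, 0.122 and 0.161 for k = 1, 2 and 4 (N = 37, 38 and 40).
- Left out, as in 9.2.7 and 11.7.2: 36 eligible patients are analysed and the type I error is 0.089.

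**Only undosed patients replaced.** N stays 36 and the type I error stays 0.089.

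**Smallest cutoff with type I error of at most 0.10, for selected N.**

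| N | Cutoff | Type I error | Power at 40% |
|---|---|---|---|
| 33 | 11 | 0.051 | 0.831 |
| 36 | 11 | 0.089 | 0.910 |
| 37 | 12 | 0.052 | 0.867 |
| 38 | 12 | 0.062 | 0.891 |
| 40 | 12 | 0.088 | 0.929 |
| 41 | 13 | 0.052 | 0.895 |
| 45 | 13 | 0.0995 | 0.955 |

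**The case against.** The strongest reply is that the passages can be read so that nothing goes wrong. Appendix D has sites send the enrollment log within 24 hours of consent, with registration following once eligibility is established. An enrolled patient found ineligible could then simply be a screening failure who was never dosed, which is the group that 11.7.3.1 replaces. The sentence in 11.7.2 also comes directly after a remark about dose-limiting toxicity, so it may have been written for Phase I evaluability. Sections 9.2.7, 11.7.2 and 11.7.3 together keep every eligible treated patient in the analysis, at worst as a non-responder. On that view nobody in this group is ever not evaluable.

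These readings are plausible, but the text does not establish them. Appendix D also speaks of patients inadvertently enrolled who are then removed from the study, so enrolment is not confined to the period before dosing. Section 11.7.3.1 does not say that it limits 11.7.2. If the 11.7.2 sentence covered only undosed patients, it would largely repeat 11.7.3.1.

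It is also fair to say that the effect is small at first: one replacement gives 0.104 against 0.10, and the larger values rest on assumed counts. That stands, and it bears on the size of the problem. The rule has no cap, however, and the excess grows with each replacement.

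Finally, 9.2.7 and 11.7.2 agree on eligible patients, so choosing all treated patients as the primary set is a judgement. An eligible-only set, applied consistently with replacement of ineligible patients, would also hold the error at 0.089 in case B. What cannot stand is to replace ineligible treated patients under 11.7.2 and also count them under 11.7.3.1.

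**Conclusion.** The concern holds. The replacement rule in 11.7.2 conflicts with 11.7.3.1 and with the scoring of unassessable patients in 9.2.7. If it is applied to treated patients, the cutoff of 11 no longer matches the number treated. For 1 to 4 replacements of treated patients without an assessable response, the type I error is 0.104 to 0.158 in place of 0.089. This assumes that the 20% null refers to all treated patients, as the intent-to-treat wording suggests, and that the replaced patients could not have responded. For treated ineligible patients who are replaced but still counted, it is 0.105 to 0.161 over the same range.

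The error stays at 0.089 if only undosed patients are replaced, if the null applies to evaluable patients only (case A), or if ineligible patients are left out (case B). The actual number of replacements is not documented. This should be fixed, with medium confidence that it would matter in practice.

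**What to change.** - Reword the sentence in 11.7.2 so that only patients who never start study drug are replaced. Remove both ineligibility and non-evaluability as grounds for replacing a treated patient. If the sentence was meant for DLT evaluability in Phase I, move it to 11.2 and say so.
- Define the primary response set as the 36 Phase II patients who start treatment, with those lacking an assessable response counted as non-responders. Use this set in 9.2.7, 11.7.2 and 11.7.3.1, and report the eligible-only result as a sensitivity analysis.
- State the cutoff in case the treated number still differs from 36: 11 for N = 33 to 36, 12 for N = 37 to 40, and 13 for N = 41 to 45.

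The cost is a few sentences and no extra patients. The observed response rate may be slightly lower. If the 40% target holds only in assessable patients, having 1, 2 or 4 unassessable patients among the 36 lowers power from 0.910 to P(X ≥ 11 | 36 − m, 0.40) = 0.888, 0.862 or 0.795 for m = 1, 2 or 4. If 40% holds in all 36 treated, power stays 0.910. Under the fallback cutoffs, power falls below 90% at some N, for example 0.867 at N = 37, so keeping the treated number at 36 is preferable.

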### **11.7.3 Discontinuation and Withdrawal of Subjects**

**11.7.3.1** All patients who initiate protocol treatment will be included in the overall evaluation of response (intent-to-treat analysis). All reasons for discontinuation of treatment should be documented clearly in the medical record. Note: Patients who sign a consent form, but do not initiate study drug will be replaced.

**11.7.3.2** Non-compliance with the study protocol; including, but not limited to not attending the majority of scheduled visits. The PI will determine when non-compliance should lead to removal from study. Note: The patients will still be included in the overall evaluation of response (intent-to-treat analysis)

**11.7.3.3** Unacceptable major toxicity. Note: The patients will still be included in the overall evaluation of response (intent-to-treat analysis).

**11.7.3.4** At patient's own request. Note: The reason for discontinuation from the study must be documented. The patients will be included in the overall evaluation of response (intent-to-treat analysis) if any protocol therapy was administered prior to withdrawal.

## **12. ETHICS**

### **12.1 Institutional Review Board**

The study protocol and any amendment that is not solely of an administrative nature must be approved by an Independent Ethics Committee (IEC) or Institutional Review Board (IRB).

### **12.2 Evaluation of benefits and risks/discomforts**

Potential **benefits**: Patients will receive evaluation and treatment of their malignancy as a result of participating in this trial. The trial will provide information on how the combination of entinostat and aldesleukin should be administered to patients, but may or may not help a specific patient personally. This treatment may offer temporary control of the disease, but is not curative by this protocol. Because of the study design, patients may be treated with a drug dose that is too low to be effective. Therefore, neither benefit can be promised nor can the chance of benefit be predicted. Alternative approaches to entering this trial, including supportive care only, will also be discussed before the verbal and written consent is obtained regarding the risks, benefits, and the treatment requirements of this trial.

**Measures for minimizing risk**: Administering entinostat and aldesleukin to patients may involve risks that are currently unforeseeable. Side effects can be unpredictable in nature and severity, although all care will be taken to minimize them. If patients suffer any physical injury as a result of participating in this study, immediate medical treatment is available at the treatment center. Frequent blood work will be taken to monitor side effects. Although no compensation is available, any injury will be evaluated and treated in keeping with the benefits or care to which patients are entitled under applicable regulations. Malignancies with no further standard treatment options generally have a poor prognosis. Therefore, patients may experience significant treatment-related morbidity, and/or complications from progression of their disease.

### **12.3 Risks/benefits analysis**

Data gathered from both clinical and laboratory evaluations in this trial will be analyzed frequently to ensure safety of patients. Any new or significant finding(s) found during the course of the research will be shared and explained to each participant since that may affect a patient's willingness to participate further. Patient's anonymity will be protected to the maximum extent in all publications and presentations that result from this research.

### **12.4 Patient information and consent**

The investigator will explain the nature of the study, its purpose and associated procedures, the

expected duration, and the potential benefits and risks of participation to each patient prior to his/her entry into the study (i.e., before examinations and procedures associated with selection for the study are performed). Each patient will have ample opportunity to ask questions and will be informed about the right to withdraw from the study at any time without any disadvantage and without having to provide reasons for this decision. Following this informative discussion, a patient will be asked if he/she is willing to sign and personally date a statement of informed consent. Only if the patient voluntarily agrees to sign the informed consent statement and has done so, may he/she enter the study. The patient will receive a copy of the signed and dated informed consent form.

The signed informed consent statement is to remain in the investigator's files. The investigator will document on each CRF that he/she has informed the patient and that the patient has signed the informed consent statement.

The informed consent form and any other written information provided to patients will be revised whenever important new information becomes available that may be relevant to the patient's consent, or there is an amendment to the protocol which necessitates a change to the content of the written informed consent form. The investigator will inform the patient of changes in a timely manner and will ask the patient to confirm continuation of his/her participation in the study by his/her signature on the revised informed consent form. Any revised written informed consent form must receive the IRB's approval/favorable opinion in advance of use.

## **12.5 Data handling and record keeping**

### **12.5.1 Case report forms**

This study has been assigned to be monitored by the Clinical Trials Monitoring Service (CTMS). Theradex is the pharmaceutical company that administers the Clinical Trials Monitoring Service. CTMS Data is required to be submitted to CTMS at least every two weeks, via the NCI/DCTD case report forms or the electronic case report form (ACES). Details on the protocol specific requirements will be communicated to the principal investigator by Theradex. Adverse event data will also be collected in the electronic data entry system used by Roswell Park Clinical Research Services. Furthermore, the investigator will document in the patient files (hospital files). If corrections are necessary, they will be entered by an authorized member of the investigator's staff in the following manner: the wrong entry will be crossed out with a single line so that it remains legible, and the correct entry will be placed next to it. All corrections will be initialed and dated by the site staff making the correction. For corrections concerning adverse events or the primary variable, a reason for any alteration must be provided.

**NCI Protocol #: 7870**

Protocol Version Date 5/29/19

page 59 of 79

Any documents related to the study must be archived at the study site or in a central archive. This includes the careful listing of the identities of the patients involved in the study. This list and the signed informed consent statements are key documents in the files to be stored by the investigator.

Patient (hospital) files will be archived according to local regulations. All documents related to the study must be retained until at least 15 years after the end of the study. At the end of this period, CTEP will inform the investigator as to when these documents no longer need to be retained.

### **12.5.2 Laboratory data and reference laboratories**

For laboratory services provided by the investigator, the investigator must supply the sponsor with a complete list of all normal laboratory values for the laboratory utilized, as well as proof of laboratory certification by the Clinical Laboratory Improvement Amendments. Shipping information for the pharmacodynamic samples is contained in section 7.6.

### **12.5.3 Patient registry**

The investigator should maintain a patient registry of all patients entered into the study in the event a safety issue arises after study completion.

### **12.5.4 Drug accountability**

The designated personnel will confirm receipt of the drugs investigational product in writing and will use the investigational product only within the framework of this clinical study and in accordance with this study protocol. He/she will keep a record of the investigational product dispensed, preferably on the CRF. The investigational product must be stored in a locked storage facility and protected from unauthorized access. Any unused, partially used, or empty containers of the investigational product will be returned to the sponsor at the termination of the study at the latest. Receipt, distribution, and return of the investigational product must be properly documented on the forms provided by the sponsor giving the following information: Study number, sender, receiver, date, mode of transport, quantity, batch number, and expire or retest date, if applicable.

